3.3. Exploratory endpoints

Exploratory stage 1

1. Changes in candidate biomarkers SOD1, Ataxin 2, C9orf72, UNC13A, TDP43, stathmin 2, NfL and NfH levels in extracellular vesicles of neuronal origin (nEVs) collected from plasma from baseline to week 4 and 8

Exploratory stage 2

1. Differences (treated vs sham) and change (from baseline to end of the study (month 6)) in biomarker levels in nEVs being informative from stage 1 collected from plasma from baseline to week 4 and 8

Hypothesis:

TPS stimulation changes molecular biomarkers levels in nEVs, which represents the cytoplasm content of brain neurons in the previous 12h, as a surrogate endpoint of the neurodegenerative process.

3.4. Safety endpoints

1. Presence of serious adverse events motor cortex excitability, reduce biomarkers of neuronal damage and slow disease progression

Hypothesis:

TPS is safe and well tolerated in patients with neurodegenerative disease and up to 80 years old

4. BACKGROUND & RATIONALE

4.1 Background

4.1.1 Therapeutic Background

Amyotrophic lateral sclerosis (ALS) is a neurodegenerative disorder that involves both upper and lower motoneurons⁴. Patients develop a progressive loss of motor function, with a mean survival of 3 to 5 years. Other brain circuits are being damaged such as frontal-temporal pathways leading to cognitive impairment and even to dementia. There is no diagnostic biomarker, and its diagnosis is based on clinical criteria, which are periodically reviewed and updated⁵⁻⁷. ALS is a heterogenous disease from the clinical, genetic, and even histopathological point of view⁸. Furthermore, there are no prognostic biomarkers that predict the outcome of the patients. New tools have even been developed to predict the progression profile of patients (ENCALS survival model, and the ENCALS risk profile) based on gender, age of onset, form, presence or absence of frontotemporal dementia, as well as respiratory function^{9, 10}. Data from sporadic and genetic forms of the disease has taught us that several key cellular and molecular pathways are involved in the disease such as cytoskeletal dynamics, neuroinflammation, mitochondrial dysfunction, reticulum endoplasmic stress and protein homeostasis^{11, 12}.

Neuromodulation is intended to activate or restore specific neuronal circuits using different types of energy at varying frequency. Invasive neurostimulation by means of deep-brain electric stimulation for Parkinson's disease and Essential Tremor have already achieved the level of validated therapies with high efficacy success and widespread usage. By contrast, the level of validation and benefits provided by non-invasive neurostimulation is very limited. For years, magnetic, electric, or light neurostimulation has been tested but has shown significant limitations because of lack of spatial resolution or low penetration into structures deep in the brain, where relevant motor circuits are located¹¹.

Transcranial Pulse Stimulation (TPS) has been shown to provide an adequate neurostimulation platform because it offers high spatial and temporal resolution, as well as the excellent safety based on decades of experience with TPS in osteo-muscular, heart and kidney diseases^{2, 3, 13, 14}. TPS can be generated with electrohydraulic, electromagnetic, and piezoelectric devices. Whereas ultrasounds uses an oscillatory sound wave, TPS uses a single sound wave (**Figure 1**). TPS can achieve significant penetration (8 cm) into the brain because of the lower skull absorption, allowing to activate the cortex, including regions further from the skull such as the hippocampus, insula or cingular cortex (**figure 2**)¹³. TPS can activate neurons by microcavitation due to the sound ultrashort waves. Such membrane displacements activate the many mechanosensors found in neurons and other cells.¹⁵ The activation of mechanosensors opens ion channels that change neuronal excitability and therefore induce either activation or

[figure not shown]

Fig.1. Ultrasound waves vs TPS waves

[figure not shown]

Fig.2. TPS beam penetrates 8 cm in the brain covering the cortex thickness

inhibition of neuronal circuits depending on the TPS protocol and the neuronal cell type¹⁶. For all these reasons, TPS has become a very promising technology for modulating neuronal circuits safely and effectively for treating brain diseases such as ALS¹⁷⁻²³.

4.1.2. TPS neuromodulation therapy

The TPS neuromodulation device (NEUROLITH) is a medical device for offline MRI-guided neuromodulation treatment that maintains brain region specific targeting based on a neuronavigation system using an electromagnetic TPS system (**figure 3**). The Neurolith system has been approved in Europe (CE mark) in 2018 for the treatment of Alzheimer disease. At present, around 10,000 patients with Alzheimer disease have been exposed to TPS with excellent safety. No serious adverse events have been reported and the most common adverse events are headache or fatigue that disappear in 24-48h. The device directly delivers the ultrashort sound beam to a key structure involved with motor modulation such as M1 cortex using a neuronavigation system (figure 2). The NEUROLITH device will be comfortably applied at the clinic visit where the patient remains sited, the hair will be humidified, and ultrasound gel is applied to the electromagnetic stimulator. The device produces a characteristic sound that is not disturbing but recognized. No heat, pain, numbness or any other sensation is perceived by the patient. The system provides a sham stimulation option based in the use of a membrane containing gas that blocks sound transmission, preserving the characteristic sound or any other feature the patient may notice.

Prior to first use, every subject will undergo an MRI scan to register the location on their temple region relative to the brain targets for tailored anatomical registration (**figure 4 and 5**). NEUROLITH has an external control unit containing a battery supply for initial cost efficiency, flexibility in stimulation protocols and human clinical study designs.

Fig.3. Neurolith device is composed by the stimulation system (control unit and power source) and neuronavigation system

Fig.4. The neuronavigation system guides TPS stimulation using off-line MRI guidance

The stimulation involves delivering 1,000 pulses per cortical region, with a maximum of 6,000 pulses per session¹³. The system uses a low energy flux density maximum of 0.25 mJ/mm² accordingly with EMA and FDA guidelines (high energy is defined as > 0.5 mJ/mm²). Each session use to extend for 20 min. The standard therapy involves 6 sessions in 2 weeks. After completion, single follow-up sessions are applied every 2 months.

4.1.3. TPS safety and operation specifications

TPS stimulation of the brain has been shown to be safe and well tolerated in animal and studies and clinical practice. So far, round 10,000 patients with Alzheimer disease have been treated with TPS (6 sessions in 2 weeks) and 800 have been retreated during follow-up (range of re-treatments 3-5) without having observed any serious adverse event¹³. Common adverse events are headaches and fatigue that disappears in 24-48h.

In addition to TPS, the field of ultrasound stimulation is providing significant amount of data supporting the safety of sound waves for neurostimulation. Multiple animal studies have analyzed histological changes of tissue following repeated ultrasound exposure within the FDA-recommended imaging limits and, to date, no studies have found evidence of tissue damage^{19, 20}. A more recent study examined long term effects of ultrasound neuromodulation in the brain using nonhuman primates²¹. The researchers treated animal's brains with focused ultrasound across 129- 147 sessions over the course of two years at a semi-regular interval. Across the study, there were no signs of behavioral degradation while performing tasks associated with the treated brain region. Furthermore, comparison of MRI brain scans before and after the two-year treatment showed no morphological abnormalities in these animals.

In addition to large animal models, histological and report-based safety data has been obtained from human neuromodulation studies. Patients scheduled for anterior temporal lobe resection for epilepsy treatment had their temporal lobe exposed to a battery of focused ultrasound paradigms prior to surgical removal²². Examination of the excised tissue revealed no indications of morphological damage or neuronal damage (acidophilic cells). In a study with ultrasound parameters comparable to those proposed here in our First-in-Human study, subjects' thalamic nuclei were stimulated to reduce pain perception. The study found a significant reduction in perception and, critically, no adverse events were reported.

4.2 Rationale

4.2.1 Rationale for the Trial and Selected Subject Population

Fig.5. The software provides controls for intensity, pulse number, pulse repetition, total number of pulses and neuronavigation

NEUROLITH is a non-invasive neuromodulation device, using low intensity TPS (LITPS) to stimulate neurons involved in motor control. LITPS stimulates neurons by cavitation that activates mechanoreceptors that modulates neuronal excitability and firing. LITPS is safe and can penetrate the skull and brain reaching the whole cortex, including deeper regions such as the hippocampus, insula or cingulate cortex. Therefore, LITPS is a highly selective neurostimulation approach to modulate relevant neuronal networks, in this case the networks regulating the motor circuits. Indeed, LITPS has shown extended effects along time²⁴.

Given the potential efficacy of LITPS, and the need for highly effective and safe treatments for ALS, this study aims to examine the safety and efficacy of LITPS to modulate motor cortex M1 in patients with ALS.

4.2.2 Rationale for Stimulation Protocols Selection/Regimen

The stimulation protocols for the current study will be 20 min duration as indicated in the CE mark approval. The system uses a low energy flux density maximum of 0.25 mJ/mm² accordingly with EMA and FDA guidelines (high energy is defined as > 0.5 mJ/mm²). The standard therapy involves 6 sessions in 2 weeks as indicated in the CE mark. After completion, single to multiple follow-up sessions can be applied every 2-3 months.

4.2.2.1 Rationale for the Use of Sham

In order to assess the efficacy of the therapy in clinical outcomes, comparison between active and sham treatment is required. Using sham or placebo for 6 months is accepted for patients with ALS as shown in the most recent phase 2 and 3 trials. In order to encourage participation and fulfill patients' expectations, sham treated patients will receive active stimulation during the open label extension period (OLE), intended to collect more safety data and to assess sustainability of the efficacy observed in the double-blinded period (DBP).

4.2.2.2 Starting Stimulation Protocols for This Trial

The stimulation protocol of TPS in this trial will start at 0.25 mJ/mm² as defined in the CE mark approval.

4.2.2.3 Maximum Dose/Exposure for This Trial

The stimulation will be always below the threshold that defines high intensity TPS (0.5 mJ/mm²) and below the threshold defined in the CE mark (0.25 mJ/mm²).

4.2.3 Rationale for Endpoints

4.2.3.1 Efficacy Endpoints

Primary endpoints:

Stage 1. Changes in the motor cortex excitability determined by TMS: neuronal hyper-excitability has been described in neurodegenerative diseases including ALS. The hyperexcitability is consider a consequence of the pathogenic process that contributes to neurodegeneration. For this reason, restoring neuronal excitability to normal limits is considered as a therapeutic target

Stage 2. Change from baseline to month 6 in the ALS functional rating scale-revised (ALSFRS-R) total score.: Changes in the ALSFRS-R is accepted primary endpoint by regulatory authorities (EMA and FDA) for defining therapeutic efficacy in this condition.

Secondary endpoints:Secondary stage 1:

1. Change in the motor cortex excitability from baseline to week 4: to assess changes in excitability in a shorter period of time (4 weeks)
2. Change plasma NfL levels from baseline to week 4 and 8
3. Changes in muscle strength, as assessed by MRC sum score and hand-held dynamometry, from baseline to week 4 and 8

Exploratory stage 1

1. Changes in candidate biomarkers SOD1, Ataxin 2, C90rf72, UNC13A, TDP43, stathmin 2, NfL and NfH levels in extracellular vesicles of neuronal origin (nEVs) collected from plasma from baseline to week 4 and 8: levels of proteins related with ALS pathogenesis in the cerebrospinal fluid (CSF) are proposed as biomarkers of the disease. nEVs is a promising strategy to identify new biomarkers. Such vesicles can be isolated from plasma (even frozen plasma) and reflects the cytoplasm content of the neuronal population 12h in advance²⁵. The vesicles content is representative of the cytoplasm and includes proteins, RNAs and metabolites. Then, nEVs can be considered as a surrogate approach to a liquid biopsy of the brain. As such, several biomarkers have been identified in patients with ALS²⁶, Alzheimer disease^{27, 28}, Parkinson disease^{29, 30}, traumatic brain injury or MS³¹. Here, we propose collecting nEVs to conduct a biomarker search study to identify biomarkers associated with the TPS therapy in the motor cortex of people with ALS. Using nEVs, we can assess such biomarkers from a blood draw sample and reflecting their content in the brain, becoming a powerful approach to validate new biomarkers for ALS and response to therapy

Secondary stage 2:

1. Differences (treated vs sham) and change (from baseline to end of the study (month 6)) in the slow vital capacity (SVC)
2. Differences (treated vs sham) and change (from baseline to end of the study (month 6)) in plasma NfL levels or other biomarkers from exploratory stage 1 if found significant
3. Differences (treated vs sham) and change (from baseline to end of the study (month 6)) in cortical hyperexcitability (MEP amplitudes, resting motor threshold, ICF and SICI)
4. Changes in muscle strength, assessed by MRC sum score from baseline to end of the study (month 6)
5. Changes in hand-held dynamometry, from baseline to end of the study (month 6)

Exploratory stage 2

1. Differences (treated vs sham) and change (from baseline to end of the study (month 6)) in biomarker levels in nEVs collected from plasma that were informative in stage 1 from baseline to week 4 and 8: same as above

4.2.3.2 Safety Endpoints

The safety and tolerability of TPS will be continuously assessed throughout the study via Adverse Event reporting, and vital signs will be assessed at every trial visit. The Columbia-

Suicide Severity Rating Scale (C-SSRS) will be conducted at the baseline and end of the treatment to prospectively assess for the emergence of suicidal ideation and behavior.

4.2.3.3 Exploratory Endpoints

4.3 Benefit/Risk

Participants in this study are patients with ALS, which due to the seriousness of their condition, have agreed to participate. TPS is not invasive, is well tolerated and is a minimal-risk device. As a result, the risk/benefit should be highly beneficial for the participants.

5.0 METHODOLOGY

5.1 Entry Criteria

5.1.1 Diagnosis/Condition for Entry into the Trial

Male and female subjects aged 21 to 80 years (inclusive) with sporadic ALS will be enrolled in this trial. Familial ALS (fALS) accounts for 10% of cases, with sporadic ALS (sALS) accounting for the remaining 90% of cases. Distinction between fALS and sALS will be done by family history.

5.1.2 Subject Inclusion Criteria

In order to be eligible for participation in this trial, the subject must:

1. Be between 21 to 80 years of age (inclusive) on the day of signing informed consent.
2. Patients with diagnosis of sporadic ALS (definite or clinically probable) as defined by the World Federation of Neurology revised El Escorial criteria⁵, SVC of 50% or greater of estimated measure and presence of cortical hyper-excitability in the motor cortex as demonstrated by TMS.
3. Each subject must sign the informed consent form, **in accordance with local requirements**, after the scope and nature of the investigation have been explained to the subject, and before Screening assessments.
4. Based on the investigator's judgment, the subject should:
 - Be able to speak, read, and understand the language of the trial staff and the informed consent form;
 - Possess the ability to respond verbally to questions, follow instructions, and complete study assessments;
 - Be able to adhere to the stimulation protocol and visit schedules.
5. Have results of a physical examination (PE), including neurological exam and vital signs not clinically significant.
6. If female, following actively anti-conceptive measures or not be of childbearing potential as indicated by one of the following:
 - Has reached natural menopause, defined as 45 years of age with ≥6 months of spontaneous amenorrhea
 - Has had a hysterectomy;
 - Has had bilateral tubal ligation; or
 - Has had a bilateral oophorectomy (with or without a hysterectomy) and greater than 6 weeks have passed since the surgery

9. Male participants must ensure a condom is used for all sexual intercourse as well as following the acceptable methods of contraception listed above for your female partner. You must ensure that they are used for the entire duration of the study. You should not father a child or donate sperm for this same period.

5.1.3 Subject Exclusion Criteria

The subject must be excluded from participating in the trial if the subject:

1. Patients with familial ALS
2. Has any unstable medical or psychiatric disease other than ET
3. Patients that are unable to tolerate TMS studies.

Additional exclusion criteria include:

1. Has evidence of a clinically relevant neurological disorder at Screening, including but not limited to: cerebellar degeneration, hyperthyroidism, multiple sclerosis, vascular dementia, Alzheimer's disease (AD), frontotemporal dementia, Huntington's disease, progressive supranuclear palsy, neurosyphilis, dementia with Lewy bodies, other types of dementia, mental retardation, hypoxic cerebral damage, cognitive impairment due to other disorders, or history of head trauma with loss of consciousness that either led to persistent cognitive deficits or in the opinion of the investigator confounds the diagnosis.
2. Is at imminent risk of self-harm, based on clinical interview and responses on the Columbia-Suicide Severity Rating Scale (C-SSRS), or of harm to others in the opinion of the investigator. Subjects must be excluded if they report suicidal ideation with intent, with or without a plan or method (e.g., positive responses to items 4 or 5 in assessment of suicidal ideation on the C-SSRS) in the past 2 months or suicidal behavior in the past 6 months.
3. Has a history of alcoholism or drug dependency/abuse within the last 5 years of Screening.
4. Has a recent history (within the 6 months prior to Screening) of regular consumption (3 or more days per week) of more than 3 alcoholic beverages per day
5. Has a recent or ongoing, uncontrolled, clinically significant medical condition where participation in the trial would pose a significant medical risk to the subject or would confound study results within 3 months of Screening, such as:
 - Conditions including but not limited to diabetes, hypertension, Human Immunodeficiency Virus (HIV) or other relevant infections, thyroid or endocrine disease, Chronic Obstructive Pulmonary Disease (COPD), delirium, congestive heart failure, angina, cardiac or gastrointestinal disease, or renal disease requiring dialysis.
 - Major surgery including not limited to abdominal, thoracic, cardiac, or orthopedic surgery, or any procedure requiring general anesthesia
 - Subjects with recently controlled or treated medical conditions may be considered for re-screening on a case-by-case basis.
 - Has a history of hepatitis or liver disease that, in the opinion of the investigator, has been active within the 6 months prior to Visit 1.
6. Has a history of malignancy occurring within the 5 years immediately before Screening, except for a subject who has been adequately treated for:
 - Basal cell or squamous cell skin cancer;
 - In situ cervical cancer;
 - Localized prostate carcinoma;

- Who has undergone potentially curative therapy with no evidence of recurrence for ≥3 years post-therapy, and who is deemed at low risk for recurrence by her/his treating physician.

7. Is pregnant, is attempting to become pregnant, or is nursing children.

8. Is or has an immediate family member (e.g., spouse, parent/legal guardian, sibling, or child) who is investigational site directly involved with this trial.

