Measurements & Procedures	
 1. ALSFRS-R 2. SVC 3. MRC sum score 4. Hand-held Dynamometry 5. Motor cortex excitability by TMS 6. Plasma NfL levels 7. Blood: isolation nEVs and biomarker quantification (SOD1, Ataxin 2, C90rf72, UNC13A, TDP43, stathmin 2, NfL and NfH) 8. Brain MRI for neuronavigation 9. TPS stimulations (6 sessions of 20 min each in 2 weeks)
Study Product / Intervention	Neurolith is a medical device delivering transcranial pulse stimulations under neuronavigation guidance.
Controls	ALS patients allocated to sham stimulations. Sham treated patients will be offered to receive TPS therapy in the Open Label Extension phase (OLE) of the trial for ethical purposes.
Number of Participants & Rationale	
Stage 1: n=10
 
Stage 2: n=40 (randomization 2:1 active vs sham stimulation)
 
Rationale for sample size: this is an exploratory sample likely to be informative for experience in planning for future trials.

Study Duration:	
24 months
 
Stage 1: 6 months
 
Stage 2: 3 months recruitment, 6 months randomized phase, 6 months OLE, 3-month analysis and clinical scientific report

Timelines:	
Stage 1:
 
 ● First Patient First Visit (FPFV): September 1st, 2024 ● Last Patient Last Visit (LPLV): February 1st, 2025 
Stage 2:
 
 ● First Patient First Visit (FPFV): March 1st, 2025 ● Last Patient Last Visit (LPLV): October 1st, 2026
Study Schedule:	
Patients are recruited from the ALS center at Hospital del Mar from patients diagnosed with ALS and referrals provided by the local ALS foundation (Miquel Valls Foundation)
 
Stage 1: V1: informed consent, inclusion/exclusion criteria, TMS cortex excitability, brain MRI (for neuronavigation) can be conducted at any time between Visit 1 and 2; V2: stim; V3: TMS and biomarkers assessment week 4; V4: TMS and biomarkers assessment week 8.

	Stage 2: V1: informed consent, inclusion/exclusion criteria, TMS cortex excitability, brain MRI (for neuronavigation) can be conducted at any time between Visit 1 and 2; V2: randomization and baseline; V3-5: stim, biomarkers and scales; V6-V7: open label extension
Study Center:	ALS center and Neuromodulation center. Hospital del Mar – Pompeu Fabra University, Barcelona, Spain

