7.1.1.5 Prior and Concomitant Treatments Review

7.1.1.5.1 Prior Treatments

The investigator or qualified designee will review any prior therapeutic drug or neurostimulation use, in advance to visit 2, and record prior treatment taken by the subject within 30 days before starting the trial.

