7.1.5.1.2 Visit 2: baseline

Patients will be randomized to either treatment or sham stimulation and assigned a code (except for patient sin stage 1, which are not randomized, and all receive active stimulation). Before starting stimulation, the researcher will conduct a vital signs, physical exam and neurological examination. Urine (50 ml) and blood (20 ml) will be collected and stored. Then, the patient will be subjected to the first TPS stimulations (a 20 min stimulations).

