8.9 Sample Size and Power Calculations

Sample size

This study will recruit 10 patients for stage 1 (open label) and 40 patients for stage 2 (randomized DBP). Using the results from the CENTAUR trial¹ in patients with ALS, a sample size of 6 patients per arm provided a 90% to detect differences by week 24 with alpha 0.05.

Power for the primary hypothesis

Considering that this is a pilot study, and no previous data is available for this intervention, a convenience sample size of 10 subjects for stage 1 and 40 for stage 2 has been defined. Using the results from the CENTAUR trial¹ in patients with ALS, a sample size of 6 patients per arm provided a 90% to detect differences by week 24 with alpha 0.05.

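### The shared eligibility list does not keep actively treated Stage 1 participants out of the sham-controlled Stage 2, so a TPS-naive sham arm is not guaranteed

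*Protocol*

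**What the plan says.** **Eligibility.** Sections 5.1.2 and 5.1.3 of the protocol serve both stages. The exclusion list begins "The subject must be excluded from participating in the trial if the subject" and has three main and eight additional items. None refers to TPS, other neuromodulation, earlier trial participation or Stage 1. The disease criteria include SVC at or above 50% of the expected value and "presence of cortical hyper-excitability in the motor cortex as demonstrated by TMS".

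**Stage 1 exposure.** Section 7.1.5.1.2 (Visit 2) describes Stage 1 patients as those "which are not randomized, and all receive active stimulation".

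**Source and timing.** Section 1.0 states "Patients are recruited from the ALS center at Hospital del Mar from patients diagnosed with ALS", together with referrals from the local foundation, and makes no distinction by stage. Stage 1 is planned to have its last visit on 1 February 2025. For Stage 2 the entry is "First Patient First Visit (FPFV): March 1st, 2025".

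**Persistence of effect.** Section 4.2.1 says "LITPS has shown extended effects along time". Section 5.2.1 spaces follow-up sessions two months apart, and the Stage 1 primary endpoint is read at week 8.

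**Prior treatment.** Section 7.1.1.5.1 asks for a review of any earlier drug or neurostimulation use before Visit 2. It then requires staff to "record prior treatment taken by the subject within 30 days before starting the trial".

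**Biomarkers.** Sections 3.2 and 3.3 carry into Stage 2 the biomarkers that were significant or informative in Stage 1.

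**The concern.** Who may be randomised is fixed in the protocol, not in a statistical analysis plan. Applied as written, the criteria admit a Stage 1 patient who still meets the SVC and TMS requirements. If such a patient is allocated to sham, that patient is not an untreated control. If allocated to active, the patient receives a second course.

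Two things are at stake. First, if some of the Stage 1 effect persists and a repeat course adds less than a first one, the active-sham difference is diluted. Second, a biomarker chosen because it moved in Stage 1 would be tested in Stage 2 partly on the patients who led to its choice, so the second look would not be independent of the first.

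**Working it through.** The plan's only sample-size figure (section 8.9: 6 per arm, 90% power, alpha 0.05) cannot be reproduced, because no effect size or SD is given. This point does not depend on it.

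**1. Does another rule close the gap?**
- Sections 7.1.1.6 and 7.1.1.7 allow one screening number and one randomisation number per subject. These are numbering rules. Stage 1 patients are not randomised, so a Stage 2 randomisation would be their first.
- Section 5.8 bars restarting treatment only for subjects who were discontinued. Stage 1 completers are not covered.
- Section 5.5 prohibits treatments named in the exclusion criteria. TPS is not named there.
- Section 8.9 counts 10 and 40 patients separately but does not say they must be different people.

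None of these is an eligibility bar.

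**2. Timing.** From 1 February to 1 March 2025 is 28 days. Stage 1 stimulation ends at about week 3 (section 6.0). For the last Stage 1 patient:
- if Stage 1 ends at week 4 (section 6.0), the final session is 7 + 28 = 35 days before Stage 2 opens;
- if it ends at week 8 (section 1.0), the final session is 35 + 28 = 63 days before.

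Patients who entered Stage 1 earlier have longer gaps. Both figures lie outside the 30-day recording window. The first is shorter than the two-month re-stimulation interval, and the second is about equal to it.

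**3. Ceiling on exposure.** 10/40 = 25% of Stage 2. If all 10 re-entered, the expected number in the sham arm would be 10 × 1/3 = 3.3 of 13.3 under the 2:1 ratio of section 1.0, or 10 × 1/2 = 5 of 20 under the 1:1 ratio of section 5.3. Either way this is 25% of the arm. (The conflict between the two ratios is a separate matter.)

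**4. Dilution.** Let m be the pre-treated share of each arm, c the fraction of the effect that persists, and a the degree to which carry-over adds to a new course (0 = not at all, 1 = fully). In units of the true effect:
- sham mean = m·c
- active mean = 1 + m·a·c
- difference = 1 − m·c·(1 − a)

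With a = 1 there is no dilution. With a = 0 the difference is 1 − m·c, the worst case:

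| Re-entering | m | c | Difference retained | Power of a design with 80% undiluted |
|---|---|---|---|---|
| 5 | 0.125 | 0.5 | 93.75% | about 75% |
| 5 | 0.125 | 1 | 87.5% | about 69% |
| 10 | 0.25 | 0.5 | 87.5% | about 69% |
| 10 | 0.25 | 1 | 75% | about 56% |

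Power is for a two-sample t test at two-sided 0.05 and is the same for 20:20 and 27:13. The values of m, c and a and the 80% starting point are assumptions, not figures from the protocol.

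**5. Chance imbalance.** Section 5.4 has no stratification. If all 10 re-entered a 20:20 trial, the hypergeometric probability of a 7:3 or more uneven split between arms would be about 0.27.

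**The case against.** The strongest reply is that re-enrolment is nowhere planned. The stages have separate counts, consent visits and timelines, and each subject gets one screening number, so separate cohorts were probably intended. That stands as a reading of intent. It makes the harm conditional, but it does not supply the missing rule.

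The dilution figure also needs conditions. If carry-over adds equally in both arms, randomisation leaves the difference unbiased. The Stage 2 endpoints are changes from a new baseline, so a stable shift left over from Stage 1 is subtracted, and only an effect that goes on altering the course to month 6 would matter for ALSFRS-R. This stands too, and is why 0.25c is a ceiling.

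Three stronger readings are tempting but not supported:
- *A reader might infer that the TMS criterion re-admits Stage 1 non-responders and so lowers the effect further.* Responders whose effect has worn off could also re-qualify, and true non-responders have little to carry over. Selection and carry-over therefore concern largely different patients and cannot simply be added. The direction and size of any selection are uncertain.
- *A reader might infer that earlier TPS would go unnoticed.* Section 7.1.1.5.1 requires a review of any prior neurostimulation before Visit 2, and the centre would know its own Stage 1 patients. Only the obligation to record is limited to 30 days.
- *A reader might infer that re-entering patients could recognise active stimulation.* Section 4.1.2 says the patient perceives no heat, pain, numbness or other sensation, and that the sham preserves the characteristic sound.

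**Conclusion.** The gap is real: no criterion bars Stage 1 participants, all actively treated, from a sham-controlled stage at the same centre that opens 28 days after the planned Stage 1 last visit. On the protocol's own claim of extended effects, any who re-enter could not be taken as TPS-naive.

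The size is bounded and conditional. At most 10 of 40 patients (25%) are involved. The active-sham difference shrinks by between 0 and 25% (0.25c, with c assumed between 0 and 1). The upper end requires that all 10 re-enter, that the whole effect persists beyond the new baseline, and that a repeat course adds nothing to it. The loss of independence for biomarkers chosen in Stage 1 holds for any re-entry, but its size cannot be computed from the document. This is a cheap improvement to the design, not evidence that Stage 2 will be biased.

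**What to change.** - In section 5.1.3, add an exclusion for Stage 2: subjects who took part in Stage 1.
- In section 7.1.1.5.1, require any prior TPS or other neurostimulation to be recorded without the 30-day limit, so that the record matches the review already required.
- If the sponsor does intend re-entry, state this in the protocol, record each patient's prior exposure, and account for it in the Stage 2 analysis, including the tests of biomarkers selected in Stage 1.

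The cost is one criterion and one case report form item. The downside is that at most 10 patients of the centre's pool become unavailable for Stage 2. If separate cohorts were always intended, nothing is lost.
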